## VII. Study Procedures and Research Design

The UG3 phase is a proof-of-concept study to test mechanistic hypotheses of the acute effects of TBS on corticothalamic inhibitory control (IC) task-based functional connectivity (tbFC), IC task performance and ad lib smoking in the laboratory while preliminarily evaluating safety and tolerability of TBS among individuals with TUD. Clearly defined milestones, focused on iTBS

versus cTBS and baseline on IC circuitry, will be met before proceeding to Phase 2 (UH3), a 4-session (over 2-weeks) randomized iTBS versus cTBS trial to assess smoking behavior over two-weeks post-treatment period.

As shown in Fig. 1, individuals ( $N=30$ ) with TUD will complete a baseline MRI visit and, using a crossover design, be randomly assigned to receive iTBS on one visit and cTBS on the other visit. Following TBS, they will repeat the protocol and then perform the SRT [4]. The effects of TBS on IC brain and behavior and smoking on the SRT, along with safety and tolerability, will be assessed.

**Strategies to Ensure a Robust and Unbiased Approach.** As detailed throughout this section, the proposed study will achieve robust and unbiased results via several design features including: explicit inclusion/exclusion criteria; randomization and blinding; use of validated measures; explicit hypotheses and well-validated analytic strategies; power estimates; and careful consideration of potential confounds. As standard practice in our laboratory, we will maximize participant retention and data collection compliance, while maximizing fidelity by providing participants with training on all task procedures prior to data collection.

Participant Retention and data collection compliance. We will minimize study drop-out and data loss due to participant burden by contacting participants 1 day prior to each session and provide session-specific details and reminders as needed. Over the study, participants will respond to digitally administered questionnaires regarding mood, craving and smoking over the past 24-hrs. This strategy has proven successful in characterizing self-report affect, craving and smoking behavior [50, 54]. In ongoing NIDA-funded smoking cessation studies by our group, response rates reach >95% following RA verification of compliance over a 4-week trial (R01DA038700); ~80% over 8-12 week trials (R34 DA042228, UG3 DA043231). The current proposed UG3 and UH3 studies both fall within a timeline where we have achieved greater than 95% participant compliance.

Training Session. Following consent, each eligible participant choosing to continue with the protocol will participate in an extensive training session to become familiar with all aspects of the study.

- Inhibitory Control (IC) Task Training. During training, participants will perform one complete 7.2 min. run of the IC task (see C.4.a.) and are required to achieve a minimum of 75% correct responses on “Go” trials and a minimum of 25% correct omissions on “NoGo” trials in order to demonstrate understanding of task instructions. If performance is sub-threshold, the participant will be provided feedback from the researcher and perform an additional practice run. Using this same training strategy in our prior studies with individuals with nicotine, cannabis, cocaine or opioid use disorder ( $N > 250$ ), > 95% of participants have met performance criteria after the 1st training run and, among those participants requiring additional training, 100% of participants met criteria after the 2nd training run.
- Habituation to Scanner Environment. Participants will practice the experimental task while inside of a mock scanner in order to reduce scan-related anxiety and improve scan data quality.
- Practice ad lib smoking. Participants will be introduced to, and practice smoking their preferred-brand cigarette using the Clinical Research Support System (CReSS) Lab smoking topography device to become familiar with smoking through the system and minimize effects of a novel smoking experience during testing.

### **Assessments, biomarkers, and self-report measures.**

- Diagnostic Assessment. A medical history and fMRI safety screening questionnaire will be conducted to ensure that the individual is eligible to participate.
- Smoking history, behavior and dependence. The following validated measures of nicotine dependence and urge to smoke will be used at various times during the study: Shiffman/Jarvik Withdrawal scale [55], Fagerström Test of Nicotine Dependence [56] & Modified Cigarette Evaluation Questionnaire [57].
- Tobacco use biomarkers. Expired air CO concentrations will be measured at screening to establish eligibility ( $CO > 10$ ) at baseline, and smoking or abstinence ( $CO < 6$ ) status prior to each experimental session, using standard procedures [33, 34]. Urinary cotinine will be used to assess quantitative measures of smoking and abstinence ( $ABS < 80$  ng/ml).
- Smoking topography. Clinical Research Support System (CReSS) Lab smoking topography device (Plowshare Technologies) will be used to assess smoking topography. Measures to be evaluated include number of puffs, puff volume (milliliters), puff duration (milliseconds), puff velocity (milliliters/second) and inter-puff interval (seconds).
- Trait and State Measures. Impulsiveness will be measured with the BIS-11 [58]. Mood state will be evaluated with the Profile of Mood States [59], which has been shown to reliably characterize the effects of abstinence on mood in dependent smokers [60, 61].
- EMA measures. Over the course of the study, participants will be prompted each day, via text messaging, to provide craving, mood ratings and quantify smoking (# cigs.) for the day through a link to a secure REDCap questionnaire and daily log of cigarettes smoked that day (see [50, 54]).
- Safety Assessment. Tolerability will be assessed using a sixteen-item review of systems (ROS) questionnaire [36] and reviewed with research team at weekly visits.

**GoGo/NoGo Inhibitory control (IC) Task.** The “GoGo/NoGo” task [4, 44] will serve as the experimental probe to evaluate the mechanistic underpinning of TBS on IC, determine whether or not to proceed from the UG3 mechanistic proof-of-concept project to the fully-powered UH3 phase. fMRI BOLD response will be collected from participants as they perform the task. Participants are instructed to press a button in response to common (gray colored circles: 75% of trials) and rare (yellow colored circles: 12.5% of trials) Go stimuli and inhibit responding to rare NoGo stimuli (blue colored circles: 12.5% of trials). The task provides errors of omission and reaction times during Go trials, controls for novelty detection during processing of rare Go trials (yellow circles) and errors of commission on NoGo trials (blue circles). Behavioral data will be processed and analyzed consistent with our prior work with this task [4]. Prior to analysis, NoGo performance will be corrected by scoring NoGo trials with null response as incorrect when the participant did not respond to the ‘Go’ trial preceding it, in order to control for lapses in attention. Data will then be analyzed in SPSS.

**Smoking Relapse analog Task (SRT).** The SRT was developed by the PI ([name]) and smoking behavior outcomes (time to lapse) shown to be predicted by IC corticothalamic neural-circuitry function [4]. In brief, the SRT is comprised of two phases. The first involves up to 10, six-minute

blocks of randomly presented trials of neutral, smoking and emotional images. Following each block, participants rate their craving on a scale from 1-10 and then choose to earn \$1 for each additional block up to 60 min., or quit the task and smoke a cigarette using a pocket CReSS system in which topography measures are recorded.

[figure not shown]
**Neuroimaging Protocol.** Imaging will be performed on a 3T Siemens Prisma scanner: a high-resolution 3D MPRAGE anatomical sequence will be acquired (matrix = 256, flip angle = 9°, 166 slices, slice thickness = 1 mm); whole brain BOLD contrast sensitive images will be acquired using a multi-band (6) EPI sequence (60 slices, TR=800 ms, TE=30 ms, FOV=216, 2.4 mm^3 voxels). Prior to the acquisition of images, the anterior and posterior commissures will be identified in the mid-sagittal slice of a localizer series, followed by the acquisition of PA and AP field maps, and then followed the acquisition of functional images during the IC task.

*fMRI IC task data preprocessing.* Similar to our prior analytic strategy using this task [4], fMRI data will be preprocessed using SPM12 to remove noise and artifacts, motion corrected [51], temporally realigned using B-spline interpolation and smoothed with an 8mm FWHM Gaussian filter. Functional images for each participant will be processed in their native space.

*IC Task Modeling.* Preprocessed data will be entered into a first-level, whole-brain analysis using the General Linear Model to examine BOLD response to each of the 5 trials of interest: NoGocorrect (successful inhibition), NoGoincorrect (error of commission), RareGocorrect (novel-target detection), RareGoincorrect (novel-target error of omission), and Goincorrect (error of omission). Each event will be modeled as a delta regressor (onset dur. = 0) and convolved with a canonical hemodynamic response function. Motion will be removed through rigid body rotation and translation and parameters included as covariates. A high-pass filter (128 seconds; .008 Hz) will be applied to remove slow signal drift. To identify successful IC-BOLD response, controlling for novelty detection, a NOGOcorrect–RareGocorrect contrast image (IC-contrast) will be generated [4] and fed forward to ROI identification.

*Region of Interest (ROI) Identification.* For each subject, the IC-contrast image will be loaded into, and overlaid onto their coregistered T1, in MRIcroGL (<http://www.mccauslandcenter.sc.edu/mricrogl/>). The PI ([name]) will train a postdoctoral fellow on how to identify the peak cluster of activation in the r.IFG (e.g. neuroanatomical boundaries, software) and, once trained, work as a team to identify ROI's with >95% agreement. The IFG is comprised of three sub-divisions—Pars opercularis, Pars triangularis and Pars orbitalis—all of which have been demonstrated to play a role in inhibitory control [52]. Across our work with TUD related disruptions in IFG activation [4, 32-35], activity in the posterior-ventral aspect of the Pars triangularis and/or posterior extent of the Pars opercularis—ventral to the inferior frontal sulcus, dorsal to lateral sulcus, anterior to the precentral sulcus—is the focal extent of the r.IFG node in the corticothalamic circuit that mediates IC and smoking relapse vulnerability [4], and is sensitive to TBS modulating IC. Thus, we have clearly defined anatomical boundaries for confining the functionally defined peak cluster that will serve as the ROI for each participant. Each participant's functionally defined ROI [as shown in Fig. 2] will be used for neuronavigating TBS.

**Neuronavigation Protocol.** Following the baseline scan and ROI identification procedure, neuronavigation will be performed using the Rogue Research Inc. © Brainsight system. First, co-registered anatomical and functional ROI data will be entered into a participant’s workflow profile, followed by skin and full-brain curvilinear reconstructions, 3-landmark identifications (bridge of nose, l.ear, r.ear), placing a pin on the ROI and coil alignment with the gyrus. The same setup parameters will be used across each of the two TBS visits and I/O BOX TTL triggers enabled to record the spatial parameters for each pulse: a) distance to target; b) target error; c) angular error; and c) twist error, for use in assessing quality control and entered as nuisance covariates in statistical analyses. In our pilot study (results shown in Fig. 1), the mean target error (i.e. shortest distance from the line projecting into the head along the coil’s path) across all conditions was 2.6 mm ( $\pm 1.0$ )—within range of the manufactures recommended threshold (3mm)—for each participants ROI (samples in Fig. 2).

*Figure 2. Individual variability in inhibitory control task-based r.IFG activation.* Randomly selected cases ( $n = 5$ ) from our pilot IC-task based fMRI-guided TBS study. Though all participants exhibited significant r.IFG activation in the IC-contrast image—similar to that reported in our prior published work [4: upper right excerpt], significant inter-subject variability in neuroanatomy along with variability in the foci of functional activation were identified above. Thus, an individual subject’s functional activity in their native space provides greater spatial specificity for targeting stimulation, as compared to using group mean activity following normalizing to an average template. *Landmarks for reference: \* = sinus; STG = Superior temporal gyrus.*

**Theta Burst Stimulation Protocols.** Following fMRI data preprocessing, modeling, ROI identification and verification (C.4.b) and setting up the neuronavigation protocol (C.4.c), participants will be randomized to receive TBS to the r.IFG on two separate experimental visits: iTBS on one visits; cTBS on one visit—counterbalanced across participants.

**Determining Resting Motor Threshold.** Standard procedures will be used to determine the participants resting motor threshold (RMT) using parameter estimation by sequential testing (PEST) procedures [53].

**Intermittent Theta Burst Stimulation (iTBS) to the r.IFG.** The total duration of the iTBS protocol [38] is 190 seconds. Participants will receive stimulation over the r.IFG (A series of 3-burst pulses presented at 5Hz, 10 pulses/sec, 10 pulses/train, 20 trains, 10.0 sec intertrain interval; 80% RMT, MagPro) using a figure 8 coil (Coil Cool B65 A/P). This protocol has been shown to enhance IC performance as shown in Figure 1.

**Continuous Theta Burst Stimulation (cTBS) to the r.IFG.** The total duration of the cTBS protocol [41] is 34 seconds. Participants will receive stimulation over the r.IFG (An intermittent series of 3-burst pulses presented at 6Hz, 18 pulses/sec, 600 pulses/train, .1 sec intertrain interval; 80% RMT, MagPro) using a figure 8 coil (Coil Cool B65 A/P). This protocol has been shown to reduced IC performance as shown in Figure 1.

**Randomization and Blinding.** This study utilizes a double-blind, crossover design with a counterbalanced (latin-square) [62] TBS condition order. Given the short—~1hr duration of the

effects of a single session of TBS on neural function and behavior [38, 41], a crossover design with a minimum of a 2-day washout period between TBS session is appropriate for this study [63]. Both the participants and the research technicians, other than the technician administering TBS, will be blinded to the condition order. At the end of each visit, the participant and the researcher will independently complete a form indicating which TBS condition they believe was administered during the session and provide a confidence rating on a scale from 1-10.

**Hypothesis Testing.** All hypothesis testing will be conducted with  $\alpha < .05$ , unless otherwise noted. **Rationale.** Based upon the tenet that iTBS induces LTP and strengthens network activity, our prior published work demonstrating that corticothalamic tbFC mediates the association between successful IC task performance and inhibiting smoking [4], and our pilot data demonstrating r.IFG iTBS improves IC (Fig. 1), we hypothesize that r.IFG iTBS will strengthen corticothalamic tbFC, improve IC and attenuate smoking lapse/relapse.

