**Aim 1. Examine the effects of iTBS on IC neural circuitry and task performance.**

**Hypothesis 1:** As compared to baseline: r.IFG iTBS stimulation will strengthen corticothalamic tbFC and improve IC task performance; whereas r.IFG cTBS simulation will weaken corticothalamic tbFC and result in worse IC task performance. **Behavioral analysis plan:** Following procedures outlined in C.4.a, IC performance data will be analyzed with a repeated-measures ANOVA to examine the effects of Condition (Baseline, iTBS, cTBS). **fMRI data analysis plan:** Following procedures in C.4.b—C.4.d, IC corticothalamic tbFC will be processed and modeled using our validated strategy [4] and then Fisher-transformed correlation coefficients (rZ) scores for each participant during each condition will be fed forward and analyzed in SPSS using a repeated-measures ANOVA to examine the effect of Condition.

**Aim 2. Examine the effects of iTBS on ad lib smoking.** **Hypothesis 2:** As compared to baseline: r.IFG iTBS, will extend the duration of abstinence; whereas cTBS shorten the duration of abstinence during an ad lib smoking lapse paradigm in the lab. **Behavioral analysis plan:** As in [4], time to initiate ad lib smoking during the SRT (see C.4.a.2) will be analyzed in SPSS using a repeated-measures ANOVA to examine the effect of Condition. Main effects of Condition on secondary smoking topography variables (e.g. puff volume (ml) and number of puffs) will be explored.

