### **Statistical Analyses**

*General Statistical Considerations.* Significance will be defined at  $\alpha = .05$ , with a cluster-determining threshold (CDT) of  $p < .001$ , as determined by Monte Carlo simulations (3dClustSim; [afni.nimh.nih.gov/pub/dist/doc/program\\_help/3dClustSim.htm](http://afni.nimh.nih.gov/pub/dist/doc/program_help/3dClustSim.htm), May 2016). Specifically, 3dcalc will take the square root of the SPM model's error variance image (ResMS) and 3dFWHMx used to empirically determine the spatial smoothness of residual error in the model using the newly developed non-Gaussian autocorrelation function (ACF). Data from the NIH, replicating the Beijing datasets [19], show that these settings, combined with CDT of  $p < .001$  and a (10mm) smoothing kernel, maintain a true false-positive rate of 5% for regular event-related designs[20].

*Experimental Inhibitory Control (IC) Task.* Data from each fMRI scan will be entered into a 1st level, whole-brain analysis using the GLM[18] to examine BOLD response to each of the 5 trial types: NoGocorrect (IC), NoGoincorrect (error of commission), RareGocorrect (correct novel-target detection), RareGoincorrect (novel-target error of omission), and Goincorrect (error of omission). Each event type will be modeled as a delta regressor at the onset of the event and convolved with a canonical hemodynamic response function. Intra-run motion will be removed through rigid body rotation and translation and parameters included as covariates. A high-pass filter (.008 Hz) will be applied to remove slow signal drift. Finally, in order to examine successful inhibitory control (IC)-related BOLD response, controlling for novelty detection, a NoGocorrect - RareGocorrect contrast image will be generated (henceforth, IC) and used for hypothesis testing. This is to be distinguished from IC accuracy, which refers to the percent of correct 'NoGo' trials achieved. Main effects of condition (iTBS vs. cTBS) on IC will be assessed via ANCOVA. Next, mean percent signal change (PSC) from 1st level models during IC will be extracted (via MARSBAR) from each of ROI within the ICN mask (Fig 4).

[figure not shown]

Figure 4: IC mask includes right inferior frontal gyrus (IFG), left precentral gyrus (BA4/M1), and bilateral thalamus (Thal), subthalamic nucleus (STN), and pre-supplementary motor area (preSMA).

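### Scoring a withheld NoGo response after a missed Go as an inhibition error reverses the bias from attention lapses instead of removing it, so a condition difference in Go omissions could appear as an inhibitory-control effect

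*Combined protocol and SAP*

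**What the plan says.** Section VII, GoGo/NoGo Inhibitory control (IC) Task, states that before analysis "NoGo performance will be corrected by scoring NoGo trials with null response as incorrect when the participant did not respond" to the Go trial before it, "in order to control for lapses in attention". The same paragraph notes that "The task provides errors of omission and reaction times during Go trials". It refers to the group's earlier work for processing and says the task will inform the decision to proceed to the UH3 phase.

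Statistical Analyses (Experimental Inhibitory Control Task) separates the BOLD contrast from "IC accuracy, which refers to the percent of correct" NoGo trials. Under Aim 1, "IC performance data will be analyzed with a repeated-measures ANOVA to examine the effects of Condition (Baseline, iTBS, cTBS"). Condition is the only factor named. No test of Go omissions by Condition, no attention covariate and no Go-accuracy floor for scanned runs is stated. The only floor is in the Training Session text, where participants are "required to achieve a minimum of 75% correct responses on" Go trials.

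IC Task Modeling labels correct NoGo trials as "successful inhibition" and incorrect ones as commission errors. It does not say whether those labels are taken before or after the re-scoring.

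**The concern.** A withheld NoGo response just after a missed Go says little about inhibition, because the participant may simply not have been responding. Crediting it as a success is wrong, but so is counting it as a failure: either way the score depends on attention. The rule chooses the second, so the score falls as lapses rise.

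What is at stake is the interpretation of Aim 1. The hypothesis is that stimulation changes inhibition. If stimulation changed arousal or task engagement instead, the planned score would move in the same way, and the planned ANOVA has no term that could tell the two apart.

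**Working it through.** **Inputs.** From the documents: the scoring rule; 30 complete datasets (Section VI); alpha .05 (Hypothesis Testing); NoGo trials as 12.5% of trials. Not in the documents, so assumed: the number of NoGo trials (50 unless stated), p = 0.6, between-subject SD 0.12, within-subject SD 0 or 0.08, and all lapse rates and lapse lengths.

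**1. The plan's own figure.** The only checkable figure on this outcome is the pilot iTBS-cTBS difference of 25.3%. From +14.4% and -8.7%: (1 + 0.144)/(1 - 0.087) - 1 = 1.144/0.913 - 1 = 25.3%. It reproduces as a ratio of relative changes. It says nothing about lapse rates.

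**2. Sustained lapses** (the missed Go and the NoGo lie in the same lapse):

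- uncorrected score: p + L(1-p), bias +L(1-p)
- planned score: p(1-L), bias -Lp
- trials dropped from numerator and denominator: p(1-L)/(1-L) = p, bias 0

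| p | L | Uncorrected | Planned | Dropped |
|---|---|---|---|---|
| 0.60 | 0.10 | 64.0% (+4.0) | 54.0% (-6.0) | 60.0% (0) |
| 0.75 | 0.10 | 77.5% (+2.5) | 67.5% (-7.5) | 75.0% (0) |

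The rule reverses the sign of the bias. Its absolute size is larger than with no correction when Lp > L(1-p), that is, when p > 0.5.

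**3. Lapses of finite length** (mean m trials). A share L/m of NoGo trials starts a lapse, is preceded by an answered Go and is still scored correct. Another share L/m is attended but follows a missed Go.

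- planned score: p(1 - L - L/m) + L/m
- all NoGo trials after a missed Go dropped: the same numerator over (1 - L)

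At p = 0.6, L = 0.10:

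- m = 5: planned 0.6 × 0.88 + 0.02 = 0.548 (-5.2 points); dropped 0.548/0.90 = 0.609 (+0.9)
- m = 3: planned 0.553 (-4.7); dropped 0.553/0.90 = 0.615 (+1.5)

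The downward bias is not universal. At p = 0.4 and m = 1.5 the planned score is unbiased: 0.4 × 0.833 + 0.067 = 0.400.

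**4. False-positive rates with no true effect on inhibition.** Paired comparison of two conditions, n = 30, 50 NoGo trials, planned scoring:

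| Lapses | 3-trial lapses, within-subject SD 0.08 | Sustained lapses, no within-subject variation |
|---|---|---|
| 5% v 10% | about 15% | about 37% |
| 5% v 15% | about 45% | about 90% |

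Dropping the trials returns about 5% in the sustained case. At 2% v 4% with 3-trial lapses and SD 0.08, the planned rule gives 6.6%.

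Three-condition repeated-measures ANOVA (within-subject SD 0.08, 30 or 50 NoGo trials, m = 3 or 5), lapses in the order baseline/iTBS/cTBS:

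| Lapses | Planned rule | All NoGo after a missed Go dropped |
|---|---|---|
| 5/5/5% | 5-6% | about 5% |
| 5/3/8% | 9-14% | 4-6% |
| 5/2/12% | 27-41% | 5-8% |
| 5/2/20% | 72-90% | 9-19% |

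Leaving the score uncorrected is no answer either: at 5/2/12% it gives 20-26%.

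**5. Which trials to drop.** Suppose missed Go trials are isolated (rate q) and the participant is attentive again at the NoGo. Dropping only the null responses gives p(1-q)/(1-qp). At p = 0.6, q = 0.10 that is 0.54/0.94 = 57.4%, because commission errors after a missed Go stay in the denominator while successes leave it. With isolated omissions of 5% v 15% up to 5% v 20%, that version gives 14-29% false positives. Dropping all NoGo trials after a missed Go gives about 5-6%.

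**The case against.** The rule is prespecified, stops lapses being credited as inhibition, and follows the group's earlier scoring, which cannot be examined here. The documents give no lapse rates and nothing to show that they differ by condition; with equal lapses the test holds its level. Go omissions and reaction times are recorded, so a difference could be looked for. All of this stands. It limits the size and certainty of the harm, but the rule still does not do what it is stated to do.

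A reader might infer more than the documents support:

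- *That lapses near 25% are to be expected.* The 75% Go criterion is a training pass mark to show that instructions are understood, and more than 95% of earlier participants met the training criteria on the first run. It does not estimate L.
- *That long visits could produce an iTBS-cTBS difference.* Both stimulation visits follow the same sequence and their order is counterbalanced. Only an effect of stimulation itself on attention could drive that contrast systematically. Visit length can matter against baseline, because the post-stimulation run is the second of its visit and the baseline visit has one run.
- *That the pilot effect was inattention.* Under sustained lapses, 25.3% would need no lapses after iTBS and 1 - 1/1.253 = 20.2% after cTBS. Nothing in the documents suggests this.
- *That the fMRI model keeps these trials among the correct NoGo trials, or that connectivity is biased.* The documents do not say which labels the model uses, and no bias in connectivity has been shown. The percent-correct definition of IC accuracy is compatible with the re-scoring and is not a rival definition.

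**Conclusion.** The concern holds, conditionally. For sustained lapses the planned score is p(1-L): it depends on attention, with the bias reversed in sign and, when p > 0.5, larger than with no correction. That is algebra and needs no assumed rate.

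The consequence for Aim 1 depends on Go omissions differing by condition. If they do, false-positive rates of about 15-37% (5% v 10%) and 45-90% (5% v 15%) follow under the stated assumptions, with the spread set by lapse length and within-subject variation. Small differences such as 2% v 4% do little. If omissions do not differ, there is no inflation. One of the two Aim 1 outcomes is affected, and the data needed for a better score are already recorded. This is a should-fix point.

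**What to change.** 1. Define IC accuracy after dropping every NoGo trial preceded by an unanswered Go, whatever the NoGo response, from both numerator and denominator.
2. Test and report Go omissions by Condition, with the number of NoGo trials dropped.
3. Keep two sensitivity analyses: the present scoring, and a version that drops only null-response trials. The second is useful because lapses that begin on the NoGo trial leave the main score slightly high (+0.9 to +1.5 points at p = 0.6, L = 10%).
4. State in IC Task Modeling and in Statistical Analyses that the dropped trials enter neither the correct nor the incorrect NoGo regressor but a regressor of no interest.

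The cost is one scoring line and some wording. There will be slightly fewer NoGo trials for inattentive participants, and less direct comparability with the group's earlier results, which retaining the present scoring as a sensitivity analysis covers. No new data are needed.
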